## Risks

### Known risks of zoledronic acid

Since this protocol was first written in 2008, there have been more publications on the potential use of bisphosphonates in children with kidney diseases including nephrotic syndrome (Gruppen et al 2013, Sbrocchi et al 2011).

ZOL is concentrated and excreted via the kidney and, like other bisphosphonates, has the potential to produce renal injury. Thus, care should be taken when administering the compound to patients with renal insufficiency. Although case reports have been published in adult medicine regarding the nephrotoxicity of ZOL with an incidence of acute kidney injury (AKI) between 9% and 13%, bisphosphonate-induced, AKI in children remains undocumented (Patzner 2008).

- In this protocol, patients are excluded if they have an estimated GFR  $< 60$  mL/min/1.73 m^2 or a rising serum creatinine increase greater than 0.5 mg/dL (44.2 μmol/L) between Visit 1 and Visit 2. Patients who have nephrotic syndrome with osteoporosis, who do not meet these exclusion criteria, have been stable for 3 months prior to enrollment, and meet the remaining eligibility criteria can be considered for this study.

Post-infusion acute phase reactions are more common after the first infusion and can include pyrexia, muscle and joint pain.

- To reduce the risk of these reactions, children will be instructed to eat and drink as usual, NSAIDs or acetaminophen (paracetamol) will be prescribed and an anti-emetic may be provided to reduce the risk of symptomatic hypocalcemia if the child develops nausea or starts to vomit. Further calcium supplements will be provided for up to 10 days at the time

of infusion and parent/guardian instructions provided on the signs to watch for as well as an emergency number, if needed.

Hypersensitivity reactions including anaphylactic reaction, anaphylactic shock, angioedema, bronchospasm and urticaria are listed in the IB. Therefore, children with a previous known hypersensitivity are excluded. Should a child develop a hypersensitivity reaction, it must be reported as an adverse event.

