		< 12 yrs	(40.0, 85.0)	If within the normal range at baseline, a value outside of normal range along with at least a 15 unit change
		12 yrs/male	(50.0, 83.0)	If within the normal range at baseline, a value outside of normal range along with at least a 15 unit change
		13 yrs/male	(50.0, 84.0)	If within the normal range at baseline, a value outside of normal range along with at least a 15 unit change
		14 yrs/male	(50.0, 85.0)	If within the normal range at baseline, a value outside of normal range along with at least a 15 unit change
		15 yrs/male	(50.0, 86.0)	If within the normal range at baseline, a value outside of normal range along with at least a 15 unit change
		16 yrs/male	(50.0, 87.0)	If within the normal range at baseline, a value outside of normal range along with at least a 15 unit change
		17 yrs/male	(50.0, 89.0)	If within the normal range at baseline, a value outside of normal range along with at least a 15 unit change
		12 yrs/female	(50.0, 82.0)	If within the normal range at baseline, a value outside of normal range along with at least a 15 unit change
13 yrs/female	(50.0, 84.0)	If within the normal range at baseline, a value outside of normal range along with at least a 15 unit change		

Laboratory parameter	Units	Age/gender range	Normal range	Criteria for clinically significant change
		14 yrs/female	(50.0, 85.0)	If within the normal range at baseline, a value outside of normal range along with at least a 15 unit change
		15 yrs/female	(50.0, 86.0)	If within the normal range at baseline, a value outside of normal range along with at least a 15 unit change
		16 yrs/female	(50.0, 86.0)	If within the normal range at baseline, a value outside of normal range along with at least a 15 unit change
		17 yrs/female	(50.0, 86.0)	If within the normal range at baseline, a value outside of normal range along with at least a 15 unit change
Heart Rate	bpm	< 12 yrs	(70.0, 130.0)	If within the normal range at baseline, a value outside of normal range along with at least a 15 unit change
		≥ 12 yrs	(50.0, 120.0)	If within the normal range at baseline, a value outside of normal range along with at least a 15 unit change
Blood Urea Nitrogen	mg/dL	≤ 17 yrs	(4.0, 24.0)	Outside the normal range
Calcium	mg/dl	> 2 - 17 yrs	(8.4, 10.3)	Outside the normal range
Chloride	mEq/L	≤ 17 yrs	(94.0, 112.0)	Outside the normal range
Creatinine	mg/dl	5 - 7 yrs/ Female	(0.2, 0.5)	Outside the normal range

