		> 7- 10 yrs/ Female	(0.2, 0.6)	Outside the normal range
		> 10 - 13 yrs/ Female	(0.3, 0.7)	Outside the normal range
		> 13 - 16 yrs/ Female	(0.4, 0.8)	Outside the normal range
		> 16 - 17 yrs/ Female	(0.5, 0.9)	Outside the normal range
		5 - 7 yrs/ Male	(0.2, 0.5)	Outside the normal range
		> 7- 10 yrs/ Male	(0.3, 0.6)	Outside the normal range
		> 10 - 13 yrs/ Male	(0.3, 0.7)	Outside the normal range
		> 13 - 16 yrs/ Male	(0.4, 0.8)	Outside the normal range
		> 16 - 17 yrs/ Male	(0.5, 0.9)	Outside the normal range

Laboratory parameter	Units	Age/gender range	Normal range	Criteria for clinically significant change
Magnesium	mg/dl	5 - 7 yrs/ Female	(1.7, 2.2)	Clinically significantly low, if < 1.0 mg/dL
		> 7- 10 yrs/ Female	(1.6, 2.2)	Clinically significantly low, if < 1.0 mg/dL
		> 10 - 13 yrs/ Female	(1.6, 2.2)	Clinically significantly low, if < 1.0 mg/dL
		> 13 - 16 yrs/ Female	(1.6, 2.3)	Clinically significantly low, if < 1.0 mg/dL
		> 16 - 17 yrs/ Female	(1.5, 2.2)	Clinically significantly low, if < 1.0 mg/dL
		5 - 7 yrs/ Male	(1.7, 2.4)	Clinically significantly low, if < 1.0 mg/dL
		> 7- 10 yrs/ Male	(1.6, 2.2)	Clinically significantly low, if < 1.0 mg/dL
		> 10 - 13 yrs/ Male	(1.6, 2.2)	Clinically significantly low, if < 1.0 mg/dL
		> 13 - 16 yrs/ Male	(1.6, 2.3)	Clinically significantly low, if < 1.0 mg/dL
		> 16 - 17 yrs/ Male	(1.5, 2.2)	Clinically significantly low, if < 1.0 mg/dL
Potassium	mEq/L	> 1 - 17 yrs	(3.4, 5.4)	Outside the normal range
Phosphorus	mg/dl	5 - 10 yrs	(3.2, 6.1)	Outside the normal range
		> 10 - 15 yrs	(3.1, 6.0)	Outside the normal range
		> 15 - 17 yrs	(2.2, 5.1)	Outside the normal range
Sodium	mEq/L	≤ 17 yrs	(132.0, 147.0)	Outside the normal range
Hemoglobin	g/dl	5 - 12 yrs/ Female	(11.2, 15.5)	Outside the normal range
		> 12 - 17 yrs/ Female	(11.6, 16.4)	Outside the normal range
		5 - 12 yrs/ Male	(11.2, 15.5)	Outside the normal range
		> 12 - 17 yrs/ Male	(12.7, 18.1)	Outside the normal range
ALT	u/L	5- 17 yrs	( 6 , 200 )	Outside the normal range
AST	u/L	5- 17 yrs	(10 , 200 )	Outside the normal range
Alkaline Phosphatase	u/L	5- 17 yrs	( 51 , 315)	Outside the normal range
Albumin	g/dL	5- 17 yrs	( 2.9 – 4.7 )	Outside the normal range
Hematocrit	%	5- 6 yrs/ Female	(35.0, 44.0)	Outside the normal range
		> 6 - 12 yrs/ Female	(34.0, 44.0)	Outside the normal range

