Patient listings will be provided for all adverse events associated with hypocalcaemia.

Laboratory parameters

The summary of laboratory evaluations will be presented with respect to three groups of laboratory tests (hematology, serum chemistry, and urinalysis).

- Hematology parameters: hemoglobin, hematocrit, red blood cell count, white blood cell count with differential counts, and platelet count.
- Serum chemistry parameters: non-fasting glucose, creatinine, serum urea, uric acid, total protein, SGOT (AST), SGPT (ALT), alkaline phosphatase, sodium, potassium, chloride, phosphorus, magnesium, albumin, calcium; and Glomerular Filtration Rate (GFR).
- Urinalysis parameters: amorphous crystals, urine bilirubin, urine blood, calcium oxalate crystals, urine color, urine glucose, urine ketone, urine leukocytes, urine nitrite, pH, urine protein dipstick, specific gravity, urine urobilinogen, and WBC Casts (Urine) /LPF.

GFR will be calculated using the Schwartz equation at all visits where serum creatinine will be measured (Visits 1, 3, 5, 6 and 8) by the Central Laboratory.

$$\text{GFR (mL/min/1.73 m}^2\text{)} = k[\text{Height (m)}]/\text{Serum Creatinine (mg/dL)}, \text{ where } k=0.41$$

Descriptive summary statistics for baseline, each post-baseline visit, and change from baseline to each visit will be presented by laboratory test group and treatment group. Note that if either the baseline or the post-baseline value is missing, then the calculation of change from baseline will also be missing.

Also, shift tables for hematology and serum chemistry will be provided in order to compare a patient's baseline laboratory evaluation relative to each study visit. For the shift tables, the normal laboratory values will be used to evaluate whether a particular laboratory test value is normal, low, or high for each visit value relative to whether or not the baseline value is normal, low, or high. These summaries will be presented by laboratory test group and treatment group.

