In addition, a summary table will be presented for the incidence rates of newly occurring clinically notable laboratory abnormalities, where patients will be counted if they have normal or missing baseline value and with at least one post-baseline assessment satisfying the clinically notable criteria. Incidence rates of newly occurring hypocalcaemia (based on central lab) by visit will be summarized similarly for patients who have normal or missing baseline level of serum calcium and clinically notable abnormal serum calcium level at each scheduled post-baseline visit. The definition of clinically notable laboratory abnormalities can be found in Appendix section "Clinically notable laboratory values and vital signs" in the protocol.

Furthermore, a summary table will be provided for the number and percentage of patients with liver enzyme abnormalities by each study visit and with at least one post-baseline assessment satisfying the liver enzyme abnormalities.

Listings of all laboratory parameter measurements will be displayed. In addition, listings of hematology and biochemistry assessments will be provided for patients with newly occurring clinically notable laboratory abnormalities. In these listings, all laboratory values will be

displayed for any patient who has at least one newly occurring clinically notable laboratory abnormality. The abnormal value will be flagged, e.g., L/H for a value being below/above normal range, and the lower and upper limit of normal values will be presented as well. Central lab calcium values will also be listed for patients with at least one post-baseline laboratory signal of hypocalcaemia and the below normal serum calcium results will be flagged as L.

For each numerical laboratory parameter, the number of decimal places to be used for laboratory values should be the same as that for the normal range. For continuous variables recorded as <lower limit>, these will be imputed as being half of the lower limit.

All laboratory parameters will be expressed using SI units.

Vital signs, [REDACTED] and weight

Descriptive summary statistics for the baseline, each study visit, and change from baseline to each study visit will be presented for sitting systolic blood pressure, sitting diastolic blood pressure, pulse rate, and body weight. [REDACTED]

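### No planned post-dose laboratory count compares a child's creatinine or GFR with that child's own baseline, so a 1.5-fold rise in creatinine, and at some ages a doubling, can be tabulated as normal

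*SAP*

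**What the plan says.** Protocol section 3.6 (Known risks) says that zoledronic acid, "like other bisphosphonates, has the potential to produce renal injury". Protocol Table 6-1 and section 6.5.4.2 schedule renal monitoring at Visits 3 and 6, 10 days after each infusion. Central creatinine and GFR are also obtained at Visits 5 and 8.

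The renal outputs planned in the SAP are these:

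- **Notable-abnormality table (Laboratory parameters).** A child is counted if the baseline value is normal or missing and there is "at least one post-baseline assessment satisfying the clinically notable criteria". The criteria come from Protocol Appendix 1. Every creatinine row there reads "Outside the normal range", and so does the single row for blood urea nitrogen (4.0 to 24.0 mg/dL). GFR has no row.
- **Shift tables (Laboratory parameters).** These cover serum chemistry, a list that includes creatinine, urea and GFR. The rule is that "the normal laboratory values will be used to evaluate whether a particular laboratory test value is normal, low, or high". Neither document gives a normal range for GFR.
- **Summaries and listings.** Change from baseline is summarised by visit and arm, and the SAP's opening section says that continuous data are shown with minimum and maximum. All laboratory values are listed.
- **Renal adverse events.** A list of MedDRA preferred terms defines the events. They are analysed with a Cox model, a log-rank test and Kaplan-Meier estimates.

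The only creatinine-change limit in either document is the rise of more than 0.5 mg/dL between Visits 1 and 2 (Protocol section 4.2, criterion 8). It applies before dosing and only to eligibility.

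**The concern.** Paired creatinine values around each infusion are collected to show whether an individual child's kidney function has worsened. The natural patient-level question is how far the child has moved from baseline. The planned counts ask instead whether the child has crossed a population limit. When the range is wide relative to the child's starting value, a large proportional rise can begin and end inside it.

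The SAP handles the other named laboratory risk differently. For hypocalcaemia, the time-to-event analysis combines adverse events with central-laboratory calcium, and there is also a laboratory incidence table by visit. The renal time-to-event analysis has no laboratory component. A laboratory deterioration enters it only after an investigator has judged it clinically significant and reported it under one of the listed terms.

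At stake is how well the tabulated comparison between arms can show individual renal deterioration, in a trial with about 46 children per arm.

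**Working it through.** The plan states no figure on this point, so there is none to reproduce. The check is arithmetic on the ten creatinine rows of Protocol Appendix 1, with lower limit L and upper limit U in mg/dL.

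Formulas for a k-fold rise:

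- Width of the range as a ratio: U/L.
- Highest in-range baseline from which the rise stays in range: U/k. The rise can stay in range only if U/k ≥ L.
- Share of in-range baselines that allow it: (U/k − L)/(U − L). This assumes baselines spread evenly over the range; the documents give no baseline distribution.

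| Age row (years) | L to U | U/L | 1.5-fold: U/1.5 | Share | 2-fold: U/2 | Share |
|---|---|---|---|---|---|---|
| 5–7, girls and boys | 0.2–0.5 | 2.50 | 0.33 | 44% | 0.25 | 17% |
| >7–10, girls | 0.2–0.6 | 3.00 | 0.40 | 50% | 0.30 | 25% |
| >7–10, boys | 0.3–0.6 | 2.00 | 0.40 | 33% | 0.30 | only at the limits |
| >10–13, girls and boys | 0.3–0.7 | 2.33 | 0.47 | 42% | 0.35 | 12.5% |
| >13–16, girls and boys | 0.4–0.8 | 2.00 | 0.53 | 33% | 0.40 | only at the limits |
| >16–17, girls and boys | 0.5–0.9 | 1.80 | 0.60 | 25% | 0.45 (below L) | not possible |

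One row in full, girls >7–10:

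- 1.5-fold: (0.6/1.5 − 0.2)/(0.6 − 0.2) = 0.2/0.4 = 50%.
- 2-fold: (0.6/2 − 0.2)/(0.6 − 0.2) = 0.1/0.4 = 25%.

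A girl of 9 who goes from 0.3 to 0.6 mg/dL has doubled her creatinine and is still in range. The notable table does not count her, and the creatinine shift table shows normal-to-normal if it uses the same range.

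Counting rows: a 1.5-fold rise can stay in range in 10 of 10. A doubling has real room in 5, fits only exactly at the limits in 3, and cannot fit in 2.

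**Sensitivity to the even-spread assumption.** Suppose instead that baselines are normal, with L and U as the central 95%, truncated to the range. The share for a 1.5-fold rise becomes 15% to 50% across rows. The share for a doubling in the five rows with room becomes about 5% to 15%.

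**What always gets out.** The ranges are 0.3 or 0.4 mg/dL wide, so any rise above 0.4 mg/dL from an in-range baseline leaves the row and is counted. A rise above 0.5 mg/dL is therefore always counted.

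**Moving up an age row.** If values are judged at the age on the visit date, which the SAP does not state, a child who changes row during the year has more room: from 2.25-fold (0.4 to 0.9) up to 3.5-fold (girls, 0.2 to 0.7).

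**Does urea close the gap?** Its range is 24/4 = 6-fold wide, so it is unlikely to.

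**The case against.** The strongest reply is that the plan is far from blind to these rises, and much of it stands.

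- A reader might infer that creatinine out of range is the only patient-level renal laboratory criterion. It is not. Urea is also a notable criterion, and the shift tables classify every child on a parameter list that includes GFR. With no GFR range in the documents, nobody can say that the GFR shift table is uninformative.
- A reader might infer that group means hide individual falls. The change-from-baseline summaries print minimum and maximum, so the most extreme change per arm and visit will be visible, and every value is listed.
- A reader might infer that detection is left to chance reporting. Protocol section 7.1 requires a review that covers significant changes from baseline as well as out-of-range values, and section 8.4 provides a DMC for safety signals.
- Blood pressure and heart rate in Appendix 1 carry a change element, which may look like a better model. In fact those rows require an out-of-range value together with a change. That is stricter, and in-range changes are not counted there either.
- Children starting below the range should be few, because Protocol section 5.5.4 expects local creatinine to be normal before the first infusion.
- No document supports a particular cut-off. At the one-decimal precision of Appendix 1, 0.2 to 0.3 mg/dL is one reporting step and already a 1.5-fold rise.

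These points limit the claim without removing it. A minimum or maximum shows one child per arm and visit. It does not show how many children deteriorated, nor the rise relative to each child's baseline. Listings contain the information but are not a comparison between arms.

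**Conclusion.** The point holds as a gap in sensitivity. Every planned post-dose laboratory count for creatinine and urea is made against normal ranges, GFR has no stated threshold, and the renal time-to-event analysis uses adverse event terms alone. A 1.5-fold rise can pass as normal in every age/sex row, for 25% to 50% of in-range baselines under an even spread (15% to 50% under the truncated normal). A doubling passes with room only at 5–7 years, in girls >7–10 and at >10–13 years, for 12.5% to 25% of baselines under an even spread. The ratios and limits are exact; the percentages depend on the assumed baseline distribution.

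Two stronger conclusions are not supported. The first is that the plan would miss most renal deterioration: under both assumptions, at least half of 1.5-fold rises from in-range baselines leave the range in every row. The second is that the trial is biased towards finding no renal effect. The same rule applies to both blinded arms and the laboratory tables are descriptive. Equal under-detection shrinks a risk difference and costs precision, but a bias between arms has not been shown.

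The change is worth making because it is cheap, concerns a named organ risk in children, and can be specified before unblinding.

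**What to change.** Before unblinding, add to the SAP under Laboratory parameters a descriptive by-arm table of children whose central creatinine rises by a pre-specified ratio to baseline. Show it for Visits 3, 5, 6 and 8 and for any post-baseline value. Ratios of at least 1.5 and at least 2 are examples; the sponsor should choose and justify the cut-offs. Give the risk difference with an exact 95% confidence interval, and list each child counted.

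Two details matter:

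- Define the count on the creatinine ratio, not on GFR. The Schwartz estimate also contains height, and children grow over 12 months, so the two are not interchangeable.
- Use unrounded or SI values. The SAP already reports laboratory data in SI units. By the protocol's own conversion (0.5 mg/dL = 44.2 µmol/L), one 0.1 mg/dL step is about 8.8 µmol/L, so SI values may carry finer resolution.

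Keep the Appendix 1 table as it is. The new table is an analysis output and sets no rule for managing patients.

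The cost is one table and one listing from data already collected. The downside is that some flags will reflect rounding at low creatinine values.

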Adverse events associated with change in renal function are defined based on predefined search list which describe a clinically significant change in renal function. A search of the clinical trial database will occur based on this pre-specified list of MedDRA preferred terms. These adverse events will be summarized by preferred term. In addition, the event rate and 25th percentile (95% CI) of time to first adverse event associated with change in renal function will be summarized. The hazard ratio and 95% CI based on a Cox proportional hazards model with treatment as a factor will be presented. Between-treatment differences in time to first adverse event associated with change in renal function will be evaluated using the log-rank test. If a patient experiences an adverse event associated with change in renal function, the event time is defined as the earliest of all events if there are multiple. Otherwise, a patient is considered censored at the last contact date. Kaplan-Meier estimates will be plotted over time if at least 1% of overall population has experienced the event.

Patient listings will be provided for all adverse events associated with clinically significant change in renal function.

Hypocalcaemia adverse events and laboratory events

Hypocalcaemia adverse events will be searched based on preferred term and summarized. Patients with reported laboratory measurements associated with a signal of hypocalcaemia will be summarized by visit. Lab hypocalcaemia (low serum calcium levels) is present if the value of serum calcium from central lab is less than the lower limit of normal range provided by the central lab.

The number and percentage of patients who met these criteria will be summarized by treatment group overall.

The event rate and 25th percentile (95% CI) of time to first hypocalcaemia occurrence based on AE and central lab calcium will be summarized. The hazard ratio and 95% CI based on a Cox proportional hazards model with treatment as a factor will be presented. Between-treatment differences in time to first hypocalcaemia occurrence based on AEs and central lab will be evaluated using the log-rank test. If a patient experiences a hypocalcaemia and low calcium value based on the central lab, the event time is defined as the earlier of these events. Otherwise, a patient is considered censored at the last contact date. Kaplan-Meier estimates will be plotted over time if at least 1% of overall population has experienced the event.

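### The by-visit table of newly occurring hypocalcaemia borrows a two-sided calcium criterion, so programmed literally it would also count newly high values

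*SAP*

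**What the plan says.** Four statements bear on this table.

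- **The table.** In the SAP, under Laboratory parameters, a general table of newly occurring notable abnormalities comes first. The text then says: "Incidence rates of newly occurring hypocalcaemia (based on central lab) by visit will be summarized similarly". A patient is counted if baseline calcium is normal or missing and there is a "clinically notable abnormal serum calcium level at each scheduled post-baseline visit". No direction is given.
- **The source of the criterion.** The next sentence reads "The definition of clinically notable laboratory abnormalities can be found in Appendix section" and points to the protocol. In protocol Appendix 1 the calcium row gives a range of 8.4 to 10.3 mg/dL for ages above 2 up to 17 years, which covers the whole trial population. Its criterion is "Outside the normal range".
- **The SAP's definition of the event.** Under Hypocalcaemia adverse events and laboratory events the SAP states: "Lab hypocalcaemia (low serum calcium levels) is present if the value of serum calcium from central lab is less than the lower limit of normal". The limit meant is the one that the central laboratory supplies. This is one-sided.
- **The companion listing.** Later in Laboratory parameters, calcium values are listed for patients with a post-baseline signal of hypocalcaemia, and "the below normal serum calcium results will be flagged as L".

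**The concern.** The rule that decides who enters the table is not the SAP's definition of hypocalcaemia. It is a general notable-value flag that is met by low or high calcium. A programmer who builds that flag for the general table and reuses it here, as the instruction to summarise similarly invites, would be following the text and would put raised calcium under a hypocalcaemia title.

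The table is likely to be read closely. The Amendment 5 rationale in the protocol records the data monitoring committee's concern about symptomatic hypocalcaemia after the first infusion, and protocol Section 5.1.2 requires calcium supplementation around each infusion. With about 46 children planned per arm, one or two misclassified children at a visit would show beside a small number of true cases.

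**Working it through.** The plan states no figure for this table, so there is none to reproduce. The check is whether the two rules classify the same values in the same way.

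**Inputs.** The range of 8.4 to 10.3 mg/dL comes from protocol Appendix 1. The documents print no separate lower limit for the central laboratory, so I take 8.4 for both rules.

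**Rules**, each applied to a child with normal baseline calcium:

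- Table rule: count if calcium < 8.4 or calcium > 10.3.
- Definition rule: count if calcium < 8.4.

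| Post-baseline calcium (mg/dL) | Table rule | Definition rule |
|---|---|---|
| 8.0 | counted | counted |
| 8.3 | counted | counted |
| 8.4 | not counted | not counted |
| 9.5 | not counted | not counted |
| 10.3 | not counted | not counted |
| 10.4 | counted | not counted |
| 10.8 | counted | not counted |

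The rules differ only above 10.3 mg/dL.

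**Can Appendix 1 be read as low-only for calcium?** Not from its text. Where the appendix means one direction it says so: every magnesium row reads "Clinically significantly low, if < 1.0 mg/dL". The calcium row has no such limit.

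**Which outputs use which rule.**

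- Two-sided as written: the by-visit table of newly occurring hypocalcaemia.
- Low-only: the summaries of laboratory hypocalcaemia by visit and overall; the time to first hypocalcaemia (Cox model, log-rank test, Kaplan-Meier plot); the flagged calcium listing.
- Low and high shown apart: the serum chemistry shift tables.
- Not based on laboratory values: the table of hypocalcaemia adverse events by preferred term.

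**Illustration of size.** The documents give no rate of high calcium. Let p be the assumed proportion of children who are newly above 10.3 mg/dL at a visit, with 46 per arm (the planned number; actual denominators would be somewhat smaller). The expected number of miscounted children per arm per visit is 46 × p, and the chance of at least one is 1 − (1 − p)^46.

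| Assumed p | 46 × p | Chance of at least one |
|---|---|---|
| 0.5% | 0.23 | 0.21 |
| 1% | 0.46 | 0.37 |
| 2.5% | 1.15 | 0.69 |
| 5% | 2.30 | 0.91 |

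**Effect on the contrast between arms.** Let a and b be the true low-calcium proportions on zoledronic acid and placebo, and h_Z and h_P the high-calcium proportions. One value cannot be both low and high, so the table would show a + h_Z and b + h_P. The difference shown is (a − b) + (h_Z − h_P). If h_Z = h_P, the difference is unchanged, but both rates are inflated and any ratio formed from them moves towards 1. If they are unequal, the difference shifts too, in a direction that the documents do not settle.

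**The case against.** The strongest reply is that the sentence does not define hypocalcaemia; it uses a term that the SAP has already defined as calcium below the lower limit. On that reading a case must be both hypocalcaemic and clinically notable. To count 10.8 mg/dL, a programmer would have to ignore the table's title, the SAP's definition and a listing that flags only low values.

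As evidence of intent this stands. A reader might infer that the SAP has settled on counting high calcium as hypocalcaemia, and the documents do not support that. Intent does not repair the counting rule, however. The sentence does not refer back to the definition, and it ties the table to a general one whose calcium flag is two-sided.

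Three further inferences also go too far:

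- **A distorted relative risk or a hidden drug signal.** Only incidence rates are planned for this table. The Mantel-Haenszel relative risk in the SAP's Adverse events section belongs to risks from the case retrieval strategy, by MedDRA level. The formal comparison of hypocalcaemia uses low calcium, and several other outputs would show the true pattern.
- **Accumulation over post-dose visits.** The table is specified visit by visit, so an ever-flagged proportion across visits does not describe it.
- **Two hypocalcaemia tables that ought to match.** The newly occurring table has a baseline condition and the other summary has none, so their counts may differ legitimately even under one definition.

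**Conclusion.** The point holds as a drafting error in a stated rule. The criterion cited for newly occurring hypocalcaemia is two-sided and conflicts with the SAP's own one-sided definition and with its listing. Taken literally, the rule would add children with newly high calcium to one descriptive by-visit safety table, which could blur the difference between arms there. No primary or secondary efficacy result depends on it, nor does the time-to-event safety comparison.

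The conflict itself rests on no assumption. Its numerical effect cannot be derived from the documents: the range of 0.23 to 2.3 miscounted children per arm per visit follows only from the assumed 0.5% to 5% and 46 per arm. The consequence is small, but the correction is worth making before the table is programmed.

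**What to change.** In the sentence on newly occurring hypocalcaemia in the SAP's Laboratory parameters section, replace the clinically notable criterion with: central-laboratory serum calcium below the lower limit of normal provided by the central laboratory. This matches the definition in the hypocalcaemia section and settles whether the laboratory's limit or the Appendix 1 figure applies. Keep the normal-or-missing baseline condition. In the general table of newly occurring notable abnormalities, give low and high calcium separate rows so that high values are still reported.

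Under this rule, 8.0 and 8.3 mg/dL are still counted, and 10.4 and 10.8 are not (again taking the lower limit as 8.4). The cost is one phrase in the SAP and one programming condition, plus a split row in the general table. No data collection, sample size or clinical rule changes. If the table has already been programmed, check which calcium flag it uses.
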